10.1 Laboratory and Point of Care Testing

688 **10.1.1 HbA1c**

687

698

716

- A blood sample (either capillary or venous draw) will be obtained at screening to obtain a baseline
- Hemoglobin A1c level. A blood test obtained within 4 weeks prior to enrollment may be used.
- HbA1c level may be measured by the study team using the DCA2000, a comparable point of care
- device, at time of screening. Labs may be obtained at a local laboratory (e.g., LabCorp, Quest)
- 693 convenient to the participant.

694 **10.1.2 Pregnancy Test**

- A serum or urine pregnancy test will be required for women of childbearing potential at in person
- of visit and admission. Test must be negative to participate in the study.

697 **10.2 Questionnaires**

10.2.1 Demographic Data Survey

- Research in diabetes technology has revealed significant disparities in minoritized population's
- representation in clinical trials and access to devices that improve diabetes outcomes. Collection
- of detailed demographic data regarding participants in technology trials has become essential. This
- includes data on race/ethnicity, income levels and insurance status, as well as education and other
- variables that describe the study population.
- The Demographic Data Survey will be electronically administered once eligibility has been met.
- 705 The below information will be gathered for all participants.
- a. Age
- 707 b. Gender
- 708 c. Race
- d. Ethnicity
- e. Martial status
- 711 f. Level of education
- g. Employment status
- 713 h. Household income
- 714 i. Health insurance status
- 715 j. Monthly insulin costs and co-payments

10.2.2 INSPIRE Questionnaire

- 717 The self-administered INSPIRE (INsulin Dosing Systems: Perceptions, Ideas, Reflections and
- Expectations) questionnaires have been developed to determine the psychosocial impact of AID

MiniNET 25-Oct-2024 Page 36 of 60

720	with T1D, as well as parents/caregivers of youth with T1D, and partners of adults with T1D.
721 722	The questionnaire will be administered at the onset of hotel admission and at the conclusion of the study.
723	10.2.3 Technology Expectations Survey
724 725 726	Participants will complete a Technology Expectation/Acceptance Survey which includes questions about attitudes, feelings, and behaviors related to the technology used in this study. AID Benefits and Burdens Scale Survey
727 728	The questionnaire will be administered prior to or at the onset of hotel admission and at the conclusion of the study.

MiniNET_25-Oct-2024 Page 37 of 60

734

739

746

755

29 Chapter 11: Risks Associated with the Clinical Trial

730 11.1 Potential Risks and Benefits of the Investigational Device

- Risks and Benefits are detailed below. Loss of confidentiality is a potential risk; however, data are
- handled to minimize this risk. Hypoglycemia, hyperglycemia and ketone formation are always a
- risk in participants with type 1 diabetes and participants will be monitored for these symptoms.

11.1.1 Venipuncture Risks

- A hollow needle/plastic tube will be placed in the arm for taking blood samples. Blood draws can
- cause some common reactions like pain, bruising, or redness at the sampling site. Less common
- reactions include bleeding from the sampling site, formation of a small blood clot or swelling of
- 738 the vein and surrounding tissues, and fainting.

11.1.2 Fingerstick Risks

- About 1 drop of blood will be removed by fingerstick for measuring blood sugars and sometimes
- HbA1c or other tests. This is a standard method used to obtain blood for routine hospital laboratory
- 742 tests. Pain is common at the time of lancing. In about 1 in 10 cases, a small amount of bleeding
- under the skin will produce a bruise. A small scar may persist for several weeks. The risk of local
- infection is less than 1 in 1000. This should not be a significant contributor to risks in this study
- as finger sticks are part of the usual care for people with diabetes.

11.1.3 Subcutaneous Catheter Risks (CGM)

- Participants using the CGM will be at minimal risk for developing a local skin infection at the site
- of the sensor needle placement. If a needle is left under the skin for more than 24 hours, it is
- possible to get an infection where it goes into the skin, with swelling, redness and pain. There may
- be bleeding where the catheter is put in and bleeding under the skin causes a bruise (1 in 10 risk).
- 751 Study staff should verbally alert the participant that on rare occasions, the CGM may break and
- leave a small portion of the sensor under the skin that may cause redness, swelling, or pain at the
- 753 insertion site. The participant should be further instructed to notify the study coordinator
- 754 immediately if this occurs.

11.1.4 Risks of Hypoglycemia

- As with any person having type 1 diabetes and using insulin, there is always a risk of having low
- blood sugar (hypoglycemia). The frequency of hypoglycemia should be no more and possibly less
- 758 than it would be as part of daily living. Symptoms of hypoglycemia can include sweating,
- 759 jitteriness, and not feeling well. Just as at home, there is the possibility of fainting or seizures
- 760 (convulsions) and that for a few days the participant may not be as aware of symptoms of
- hypoglycemia. A CGM functioning poorly and significantly over-reading glucose values could
- 762 lead to inappropriate insulin delivery.

MiniNET 25-Oct-2024 Page 38 of 60

11.1.5 Risks of Hyperglycemia

Hyperglycemia and ketonemia could occur if insulin delivery is attenuated or suspended for an extended period or if the pump or infusion set is not working properly. A CGM functioning poorly and significantly under-reading glucose values could lead to inappropriate suspension of insulin delivery.

11.1.6 Risks of Device Reuse

- Participant will be informed that FDA or relevant national authorities have approved the insulin pump, CGM, glucometer and ketone meter for individual use and that by using them among multiple patients, bloodborne pathogens (i.e. Hepatitis B) may be spread through the use of multiple users.
- 773 The study CGM system is labelled for single patient use only. The sensor (the component of the system that enters the skin) will be individual use only. The transmitter and receiver may be reused during the study after the study team cleans the device using a hospital-approved cleaning
- procedure. The transmitter is attached to the sensor but does not enter the skin and the receiver, if
- used, is a handheld device.
- 778 CGM cleaning instructions are provided in the Dexcom G4 Platinum (Professional) Cleaning and
- 779 Disinfection manual (current edition) and a similar approach will be applied for the CGMs used in
- 780 this study.
- 781 The study insulin pumps are labelled for single patient use. During the study, this device may be
- reused after the study team cleans the device with a hospital-approved cleaning procedure. All
- infusion set equipment will be single patient use only (infusion set insertion kits, tubing, cartridges
- 784 etc.)

789

763

764

765766

767

768

769

770

771

772

- 785 The study-provided blood glucose meter will be returned to the study participant at the conclusion
- of the study after the study team has confirmed data collection. The study team will use cleaning
- procedures if it is necessary to be in physical contact with the equipment to download the device.
- 788 The study team will clean the ketone meter per manufacturer directions.

11.1.7 Device Cleaning Instructions

- Members of the study team will clean the study equipment after use as noted in these instructions.
- 791 CGM cleaning instructions are provided in the Dexcom G4 PLATINUM (Professional) Cleaning
- and Disinfection manual (current edition). The transmitter should be cleaned with Clorox
- 793 Healthcare® Bleach Germicidal Cleaner or any disinfectant product in a spray bottle containing a
- bleach solution of 6500 parts per million with the EPA registration number 56392-7. The
- 795 transmitter will be submerged in this solution and then placed on an absorbent wipe or clean
- surface. Two sprays will be dispensed from the Clorox cleaner onto each side of the transmitter.
- 797 A nylon brush will be used to scrub the transmitter on all sides for 30 seconds. The transmitter

MiniNET 25-Oct-2024 Page 39 of 60

- 798 will be placed in the Clorox Cleaner solution for one minute. The transmitter is then rinsed under 799 flowing tap water for ten seconds. The transmitter will then be disinfected using a disinfectant product with EPA registration number 56392-7 using similar procedures as the cleaning process. 800 801 Per the pump manufacturer, the insulin pump will be cleaned with a damp lint-free cloth. Use of 802 household or industrial cleaners, solvents, bleach, scouring pads, chemicals, or sharp instruments 803 are prohibited. The pump should never be submerged in water. If needed, use only a very mild 804 detergent, such as a bit of liquid soap with warm water. A soft towel will be used to dry the pump. 805 The glucometer is cleaned and disinfected with two separate Super Sani-Cloths (EPA number 806 9480-4). The entire surface will be cleaned, making sure the surface stays wet for 2 minutes. This 807 step is repeated with a clean cloth for disinfecting the device. 808 The Precision Xtra User's Guide suggests that healthcare professionals use 10% bleach, 70% 809 alcohol or 10% ammonia to clean the device. 810 Equipment that touches intact skin will be cleaned with ethyl or isopropyl alcohol (70-90%), quaternary ammonium germicidal detergent (i.e. Cavicide, EPA number 46781) or household 811 812 bleach. The contact time on the surface depends on the method used to clean the equipment. 813 Cavicide requires three minutes on the surface of the equipment. Clorox Germicidal Bleach Wipes 814 require two minutes on the equipment. The surface should remain wet (i.e. slightly damp) with the 815 disinfectant to be considered effective though not wet enough to leave drops of liquid. 816 In the event a manufacturer updates cleaning procedures for their device, the study team will 817 adhere to the most current recommendations. 818 There is the risk of blood sampling collection and contamination from sampling techniques. Hand 819 washing with either soap & water or waterless hand sanitizer will be used prior to caring for the 820 study subject. Gloves will be worn during blood sample collection and processing. Medical personnel will continue to practice hygiene for the subject's protection (i.e. hand washing, 821 822 changing gloves frequently, disposing needles properly). Gloves will be removed, and hands 823 washed or sanitized prior to leaving and upon return to the subject's room. Soiled linen will be
 - 11.1.8 Hb1Ac Risk

changed to minimize the transfer of pathogenic organisms.

824

825

826

827

828

829

830

831

An NGSP Point of Care analyzer (i.e. DCA Vantage Analyzer) will be utilized at the research site to obtain the subject's HbA1c level.

11.1.9 Other Risks

Some participants may develop skin irritation or allergic reactions to the adhesives used to secure the CGM, or to secure the insulin infusion sets for the continuous subcutaneous insulin infusion. If these reactions occur, different adhesives or "under-taping" (such as with IV 3000, Tegaderm,

MiniNET 25-Oct-2024 Page 40 of 60

- etc.) will be tried, sites will be rotated frequently, and a mild topical steroid cream or other
- medication may be required.
- Whenever the skin is broken there is the possibility of an infection. The CGM and pump infusion
- sites are inserted under the skin. It is possible that any part that is inserted under the skin may cause
- an infection. These occur very infrequently, but, if an infection was to occur, oral and/or topical
- antibiotics can be used. The risk of skin problems could be greater if you use a sensor for longer
- than it is supposed to be used. Therefore, participants will be carefully instructed about proper use
- 839 of the sensor.
- Data downloaded from the CGM, insulin pump, glucometer, and ketone meter will be collected
- 841 for the study as measures of diabetes self-management behaviors. Some people
- may be uncomfortable with the researchers' having such detailed information about their daily
- 843 diabetes habits.

844

848

860

11.1.10 Known Potential Benefits

- 845 It is anticipated that this protocol will yield increased knowledge about using an automated
- closed-loop system with anticipatory action to control glucose levels. The individual participant
- may not benefit from study participation.

11.1.11 Risk Assessment

- Based on the facts that (1) adults and adolescents with diabetes experience mild hypoglycemia and
- 850 hyperglycemia frequently as a consequence of the disease and its management, (2) the study
- intervention involves periodic automated insulin dosing that may increase the likelihood of
- 852 hypoglycemia, and periodic automated attenuation of insulin delivery that may increase the
- likelihood of hyperglycemia, (3) mitigations are in place, and have been tested in prior studies
- using the investigational device system in the home setting, that limit the likelihood of excessive
- insulin dosing or prolonged withdrawal of insulin, and (4) rapid reversal of hypoglycemia and
- 856 hyperglycemia can be achieved, it is the assessment of the investigators that this protocol falls
- under DHHS 46.405 which is a minor increase over minimal risk. In addition, it is the belief of the
- 858 investigators that this study also presents prospects of direct benefit to the participants and general
- benefit to others with diabetes.

11.2 General Considerations

- The study is being conducted in compliance with the policies described in the study policies
- document, with the ethical principles that have their origin in the Declaration of Helsinki, with the
- protocol described herein, and with the standards of Good Clinical Practice (GCP).
- Whenever possible, data will be directly collected in electronic case report forms, which will be
- considered the source data.

MiniNET 25-Oct-2024 Page 41 of 60

866

867

868

The protocol is considered a significant risk device study, due to the fact that the closed loop system is experimental. Therefore, an investigational device exemption (IDE) from the U.S. Food and Drug Administration (FDA) is required to conduct the study.

MiniNET_25-Oct-2024 Page 42 of 60

Chapter 12: Adverse Events, Device Issues, and Stopping Rules

12.1 Definitions

12.1.1 Adverse Events (AE)

- Any untoward medical occurrence in a study participant, irrespective of the relationship between
- the adverse event and the device(s) under investigation (section 12.2) for reportable adverse events
- for this protocol).

876

877

878

879

880

881

882 883

884

885

886 887

888

889

890

891

892

893

894

895896

897

898

899

900

901

Positive pregnancy test will not be considered an adverse event.

12.1.2 Serious Adverse Event (SAE)

- Any untoward medical occurrence that:
 - Results in death.
 - Is life-threatening; (a non-life-threatening event which, had it been more severe, might have become life-threatening, is not necessarily considered a serious adverse event).
 - Requires inpatient hospitalization or prolongation of existing hospitalization.
 - Results in persistent or significant disability/incapacity or substantial disruption of the ability to conduct normal life functions (life threatening).
 - Is a congenital anomaly or birth defect.
 - Is considered a significant medical event by the investigator based on medical judgment (e.g., may jeopardize the participant or may require medical/surgical intervention to prevent one of the outcomes listed above).

12.1.3 Unanticipated Adverse Device Effect (UADE)

Any serious adverse effect on health or safety or any life-threatening problem or death caused by, or associated with, a device, if that effect, problem, or death was not previously identified in nature, severity, or degree of incidence in the investigational plan or application (including a supplementary plan or application), or any other unanticipated serious problem associated with a device that relates to the rights, safety, or welfare of participants (21 CFR 812.3(s)).

12.1.4 Adverse Device Effect (ADE)

Any untoward medical occurrence in a study participant which the device may have caused or to which the device may have contributed.

12.1.5 Device Complaints and Malfunctions

A device complication or complaint is something that happens to a device or related to device performance, whereas an adverse event happens to a participant. A device complaint may occur independently from an AE, or along with an AE. An AE may occur without a device complaint or there may be an AE related to a device complaint. A device malfunction is any failure of a device

MiniNET 25-Oct-2024 Page 43 of 60

to meet its performance specifications or otherwise perform as intended. Performance specifications include all claims made in the labeling for the device. The intended performance of a device refers to the intended use for which the device is labeled or marketed. (21 CFR 803.3).

12.2 Reportable Events

For this protocol, a reportable adverse event includes any untoward medical occurrence that meets one of the following criteria:

- A serious adverse event as defined in section 12.1.2.
- An Adverse Device Effect as defined in section 12.1.4, unless excluded from reporting in section 12.7.
- An Adverse Event as defined in section 12.1.1 occurring in association with a study procedure.
- An AE as defined in section 12.1.1 which leads to discontinuation of a study device for 4 or more hours during the hotel phase and 12 or more hours during the at home phase.
- Hypoglycemia meeting the definition of severe hypoglycemia as defined in section 12.2.1
- Diabetic ketoacidosis (DKA) as defined in section 12.2.2 or in the absence of DKA, a hyperglycemic or ketosis event meeting the criteria defined below.

Hypoglycemia and hyperglycemia not meeting the criteria below will not be recorded as adverse events unless associated with an Adverse Device Effect. Skin reactions from sensor placement are only reportable if severe and/or required treatment.

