 - 9. If participant capable of becoming pregnant, must agree to use a form of contraception to prevent pregnancy while a participant in the study (e.g. hormonal contraception, abstinence from heterosexual intercourse). A negative serum or urine pregnancy test will be required for all females of childbearing potential. Participants who become pregnant will be discontinued from the study. Also, participants who during the study develop and express the intention to become pregnant within the timespan of the study will be discontinued.
 - 10. Willingness to use the study FCL system (CGM, pump, and phone) during the relevant study period.
 - 11. Willingness not to start any new non-insulin glucose-lowering agent during the course of the trial.
 - 12. Willingness to participate in all study procedures including the house/hotel session, exercise challenges (e.g., one hour per day during hotel), and to consume approximately 3 unannounced meals per day during the relevant portion of the supervised hotel session.
 - 13. Access to internet at home and willingness to upload data during the study as needed.
 - 14. Investigator has confidence that the participant can successfully operate all study devices and is capable of adhering to the protocol.
 - 15. Participant is proficient in reading and writing English.

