12.2.1 Hypoglycemia Event

Hypoglycemia not associated with an Adverse Device Effect is only reportable as an adverse event when the following definition for severe hypoglycemia is met:

- The event required assistance of another person due to altered consciousness, and required another person to actively administer carbohydrate, glucagon, or other resuscitative actions.
- Impaired cognitively to the point that he/she was unable to treat himself/herself, was unable to verbalize his/ her needs, was incoherent, disoriented, and/or combative, or experienced seizure or coma. These episodes may be associated with sufficient neuroglycopenia to induce seizure or coma.
- If plasma glucose measurements are not available during such an event, neurological recovery attributable to the restoration of plasma glucose to normal is considered sufficient evidence that the event was induced by a low plasma glucose concentration.

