12.3 Relationship of Adverse Event to Study Device

- The study investigator will review each adverse event and assess the relationship of any adverse
- event to be related or unrelated by determining if there is a reasonable possibility that the adverse
- event may have been caused by the study device.
- To ensure consistency of adverse event causality assessments, investigators should apply the following general guideline when determining whether an adverse event is related:
 - RELATED: There is a plausible temporal relationship between the onset of the adverse event and the study intervention, and the adverse event cannot be readily explained by the participant's clinical state, intercurrent illness, or concomitant therapies; and/or the adverse event follows a known pattern of response to the study intervention; and/or the adverse event abates or resolves upon discontinuation of the study intervention or dose reduction and, if applicable, reappears upon re-challenge.
 - UNRELATED: Evidence exists that the adverse event has an etiology other than the study intervention (e.g., preexisting medical condition, underlying disease, intercurrent illness, or concomitant medication); and/or the adverse event has no plausible temporal relationship to study intervention.

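### Section 12.2 gives two conflicting recording rules for glucose events that stop a study device, arise in a study procedure or (rarely) are SAEs, when they are not judged device effects and fall outside 12.2.1 and 12.2.2

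*Combined protocol and SAP*

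**What the plan says.** Section 12.2 opens with an any-one-of list: "For this protocol, a reportable adverse event includes any untoward medical occurrence that meets" one of six criteria. Four are general: an SAE; an Adverse Device Effect (ADE), subject to 12.7; "An Adverse Event as defined in section 12.1.1 occurring in association with a study procedure"; and "An AE as defined in section 12.1.1 which leads to discontinuation of a study device for 4 or more hours" in the hotel, or 12 or more hours at home. The other two are specific to glucose: severe hypoglycemia (12.2.1), and DKA or a qualifying hyperglycemia or ketosis event (12.2.2).

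The section then closes with: "Hypoglycemia and hyperglycemia not meeting the criteria below will not be recorded as adverse events unless associated with an Adverse Device Effect". The criteria it points to are those of 12.2.1 and 12.2.2. Section 12.2.1 repeats the restriction: "Hypoglycemia not associated with an Adverse Device Effect is only reportable as an adverse event" when the severe hypoglycemia definition is met. Section 12.2.2 has a parallel lead-in with four criteria: DKA, care at a health care facility, ketones of at least 1.5 mmol/L with provider contact, or ketones of at least 3.0 mmol/L.

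The exception turns on 12.1.4, which defines an ADE as "Any untoward medical occurrence in a study participant which the device may have caused or to which the device may have contributed". Section 12.3 guides attribution; one ground for calling an event unrelated begins "UNRELATED: Evidence exists that the adverse event has an etiology other than the study intervention (e.g., preexisting medical condition, underlying disease".

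**The concern.** For most adverse events the six bullets decide whether a form is completed. For a low or high that meets only the discontinuation, study-procedure or SAE bullet, the list says report, while the closing sentence and the lead-ins say do not record unless the event is associated with an ADE. Two people following the protocol in good faith can therefore reach opposite answers on the same event.

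Glucose events are the main harm that a trial of an insulin-dosing algorithm is meant to observe, and a plausible reason for a participant to come off the system. The plan aims for six completers, so a single glucose-driven discontinuation without an adverse event form would be a visible hole in the safety account. The ADE exception does not settle the matter. It makes recording depend on attribution, although 12.1.1 defines an adverse event without regard to its relationship to the device.

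**Working it through.** No arithmetic applies: the point concerns which rule governs, and the documents give no event rate. The check sets the two rules side by side for six event types. In rows 1 to 5 the event is not judged an ADE.

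| Event | Bullets of 12.2 | Closing sentence with 12.2.1 / 12.2.2 | Result |
|---|---|---|---|
| 1. Non-severe low during the Day 2 walk | Study-procedure bullet: report | Not severe: do not record | Conflict |
| 2. Low or high that stops a study device for 4 h or more (hotel) or 12 h or more (home), outside 12.2.1 / 12.2.2 | Discontinuation bullet: report | Do not record | Conflict |
| 3. High that is an SAE treated in hospital | SAE bullet: report | Facility criterion of 12.2.2: report | Agree |
| 4. Low that is an SAE with seizure, coma or inability to self-treat | SAE bullet: report | Severe hypoglycemia: report | Agree |
| 5. Low that is an SAE by hospitalization or investigator judgment, without the 12.2.1 features | SAE bullet: report | Do not record | Conflict, narrow |
| 6. Any of these, judged an ADE | ADE bullet: report | Exception applies: report | Agree |

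Row 1 depends on the walk being a study procedure. Chapter 12 does not define the term, but inclusion criterion 12 in 3.4 reads "Willingness to participate in all study procedures including the house/hotel session, exercise challenges", which supports that reading.

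Row 2 can arise from the protocol's own instructions. Under 7.6.1(c), a participant with any sign of neuroglycopenia, lethargy being the first example, is treated and leaves the study. That ends device use, so either time threshold is passed. Section 12.2.1 asks for more: another person's help because of altered consciousness, or impairment such as inability to self-treat, incoherence, disorientation, seizure or coma. A lethargic participant who takes oral glucose unaided can leave the trial without meeting it. The discontinuation bullet then requires a form; the closing sentence excludes one unless the low is classed as an ADE.

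The order of decisions also matters. Under 12.2.2 the Medical Monitor reviews completed adverse event forms, and under 12.5 the Monitor's view on causality prevails. Review at the time of occurrence (Chapter 9 and 12.10) covers DKA, severe hypoglycemia and device-related serious events. An ADE short of a UADE goes to the Monitor under Chapter 9 at the principal investigator's request. If a non-severe low is judged not to be an ADE before any form exists, the check in 12.5 has nothing to act on.

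**The case against.** The strongest reply is that a specific rule carved out of a general list is ordinary drafting. The next sentence of 12.2 does the same for skin reactions, and it is sensible not to complete a form for every routine low in type 1 diabetes. The ADE exception appears in all three places and 12.1.4 is broad, so a low or high under algorithm dosing that takes the system off will often be recorded anyway. Calling an event unrelated under 12.3 requires evidence of another cause or no plausible temporal relationship. All of this stands, and it limits the point to events not judged ADEs. It does not say which rule prevails for those events.

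A reader might infer three stronger things that the documents do not support.

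- That the closing sentence cancels the section's criteria. It does not: the ADE, severe hypoglycemia and DKA or ketosis bullets are untouched, and rows 3 and 4 show that most glucose SAEs are recorded under either rule.
- That any suspension of closed loop triggers row 2. The bullet concerns a study device, and pump and CGM can continue in open loop (2.6, 7.9). The glucose-driven suspension in 7.6.2 and 7.9 is about four hours and adjustable. It may touch the hotel threshold but would not ordinarily reach the home one.
- That glucose harm goes unseen. CGM time below 54 and 70 and above 250 mg/dL, the exercise and meal metrics (14.3.2), the assessment of lows (14.4), the automated alerts and recorded contacts (8.2), the check-in review of values below 60 and above 300 mg/dL (8.4) and the percent time in closed loop (14.6) all remain. The cause of lost hours may often be recoverable from these, but none of them requires a glucose event to be linked to a discontinuation.

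**Conclusion.** The point holds in a limited form. For a glucose event that is not judged an ADE and is outside 12.2.1 and 12.2.2, section 12.2 both requires and excludes recording when the event stops a study device for the stated time, is associated with a study procedure, or, rarely, is an SAE. Three of the six event types checked conflict.

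The number of events affected cannot be estimated. The documents give no rate for these events, and a count of all lows on the system would not measure them. The consequence is an incomplete adverse event record and a missing link between a glucose event and a discontinuation, not a loss of safety data overall. Section 14.4 specifies no analysis of adverse event counts, so no planned estimate changes.

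The conclusion assumes that the criteria in the closing sentence are those of 12.2.1 and 12.2.2, that the exercise challenge counts as a study procedure, and that 7.6.1(c) is applied as written.

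**What to change.** Amend the closing sentence of 12.2 and the lead-ins of 12.2.1 and 12.2.2 so that a hypo- or hyperglycemia event that is an SAE, or that leads to study-device discontinuation of the length already stated, is always recorded as an adverse event, whatever its attribution. State explicitly whether the study-procedure bullet applies to non-severe glucose events, so that a low on the walk has one answer.

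Leave the ADE definition in 12.1.4 as it is. Limiting it to malfunction or use error would drop lows caused by the algorithm dosing as designed, which is the behavior under test. No change to 12.3 is needed, because once these events are recorded their attribution goes through 12.5.

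The cost is a few sentences in three sections and a few more adverse event forms.
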